5.2.1 Inclusion Criteria

Subjects meeting all of the following criteria are eligible to participate in this study:

1. Male and female subjects aged ≥ 18 years. For a country where the legal age of consent is >18 years old, the country requirements should be followed.
2. Test positive for influenza A by rapid antigen test or with another commercially available test on an adequate nasopharyngeal specimen in accordance with the manufacturer's instructions, or an acceptable local test including, PCR, FIA, or ELISA.
3. Onset of influenza symptoms no more than 5 days before VIS410/placebo infusion; symptoms may include cough, dyspnea, sore throat, fever, myalgias, headache, nasal symptoms (rhinorrhea, congestion), fatigue, diarrhea, anorexia, nausea, and vomiting.
4. Requirement for oxygen support including any positive pressure ventilation (PPV).
5. Women of childbearing potential must have a negative pregnancy test within 2 days prior to VIS410/placebo infusion.
6. Women should fulfill one of the following criteria:
 - a. Post-menopausal: either amenorrhea ≥ 12 months or follicle stimulating hormone > 40 mIU/mL as documented in their medical history
 - b. Surgically sterile; hysterectomy, bilateral oophorectomy, or tubal ligation
 - c. Women of childbearing potential participating in heterosexual relations must be willing to use adequate contraception from screening until 60 days post-VIS410/placebo infusion (see Section 6.2).
7. Non-vasectomized (or vasectomized less than 6 months prior to dosing) male subjects who have a female partner of childbearing potential must use an effective birth control method (see Section 6.2) when having heterosexual intercourse, from screening until 60 days post-VIS410/placebo infusion.
8. Subject is able and willing to comply with study procedures, as per protocol.
9. Subject, or a legally acceptable representative, is able to understand the purpose and risks of the study and willing to give voluntary written informed consent.

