## 4 GENERAL ANALYSIS DEFINITION

### 4.1 General Considerations

All statistical analyses and summary information are to be generated according to this SAP. Any deviations from this SAP will be documented in the clinical study report (CSR).

These descriptive statistics will be presented for continuous parameters: the number of subjects used in the calculation (n), mean, standard deviation (SD), median, minimum, and maximum values. For PK parameters, the geometric mean and coefficient of variance (CV) will also be presented. All continuous summaries will display the minimum and maximum value with the same number of decimals collected in the data. The median, mean, geometric mean and CV will display 1 additional decimal, and the SD and SE will display 2 additional decimals. For categorical variables, frequencies and percentages will be reported. All percentages will be reported to 1 decimal; all p-values will be reported to 3 decimals.

All temperature measurements will be presented as degrees Celsius. Degrees in Fahrenheit will be converted with this formula:

$$T_C = (T_F - 32) * (5/9),$$

where  $T_C$  is a Celsius temperature and  $T_F$  is a Fahrenheit measurement.

Since this is a phase 2 study rigorous control over type 1 error will not be used; all statistical comparisons will be performed using 2-sided tests at the 0.05 significance level, unless specifically stated otherwise. All null hypotheses will be defined as no treatment difference. All p-values are presented for informational purposes only; there will not be any adjustments for multiple comparisons.

All analyses, summary tables, figures, and data listings will be generated with SAS version 9.4 or higher. Specialized PK software will be used for some PK analyses.

Baseline is defined as the latest non-missing measurement taken prior to study drug administration.

January 17, 2019

All summaries will be by actual visit, no visit windows for analysis will be defined. In general, summaries will be by treatment groups, and will include a combined VIS410 treatment group, in addition to the individual low dose (2000 mg) VIS410, high dose (4000 mg) VIS410, and Placebo treatment groups, unless specified differently. Summaries of disposition, other baseline data, and adverse events will also include an overall column.

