### **9.2.8 Nasopharyngeal Viral Load**

Standard non-compartmental approaches using Phoenix WinNonlin (Certara, Princeton, NJ, USA; Version 7.0 or higher) will be used to calculate nasopharyngeal viral load (VL) parameters. Viral load at each study visit, proportion of subjects with negative results at each study visit, peak VL, and VL AUC based on qRT-PCR and TCID50 from nasopharyngeal secretions will be summarized with n, mean, SD, geometric mean, CV, minimum and maximum values in the MITT population overall and per influenza A virus subtype. All available viral data within the MITT population will be assessed to calculate proportion of subjects with negative results at each study visit. For all other calculated parameters, viral load will be assessed on all samples in the MITT population collected through Day 7 for TCID50 and Day 14 for qRT-PCR.

January 17, 2019

Viral shedding by qRT-PCR or TCID50 versus time and VL AUC will be assessed using baseline-adjusted and non-adjusted comparisons. Each of the analyses described above will also be performed for the MITT subgroup comprised of all MITT subjects with a positive baseline-positive influenza viral culture result. In addition, VL and VL AUC by qRT-PCR for the first 50 subjects will be listed through Day 28 if subject is qRT-PCR positive on Day 14 and the Day 28 sample is tested by qRT-PCR (no summary statistics will be presented). For missing data on Day 1 post-dose, Day 3, Day 5 and Day 7, the analysis will be conducted without imputation and with the last observable measurement carried forward (LOCF). For missing data on Day 1 predose, the analysis will be conducted by replacing the missing data with the Day 1 postdose observable measurement. Subjects missing both Day 1 predose and Day 1 postdose will be removed from the analysis. Some parameters will also be analyzed using baseline-adjusted values. Viral load data will be normalized by dividing the value by the baseline value.

ANOVA will be used to assess the difference between treatment groups in the VL AUC from nasopharyngeal swabs based on qRT-PCR and TCID50. If the assumptions needed for ANOVA are not met, log transformation and/or non-parametric methods will be used. Differences between groups in peak post-baseline VL (qRT-PCR and TCID50) will be tested, and the proportion of subjects with peak VL (by qRT-PCR and TCID50) occurring post-baseline.

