Several methods will be considered to assess the potential impact of baseline viral load (qRT-PCR and TCID50) on viral load AUC. Division of AUC by baseline viral load followed by ANOVA will be used as an initial measure of baseline viral load impact. In addition, an ANCOVA model may be used. The model will be evaluated with treatment as a fixed effect and baseline viral load as a continuous covariate. Each VIS410 dose group and the combined VIS410 total group will be compared to placebo.

Chi-square methods will be used to compare differences in treatment groups relative to placebo for the proportion of subjects with negative results on Day 3, Day 5 and Day 7 study visits.

For the influenza A virus subtype H3, virus load data measured by TCID50 will be read out by both hemagglutination and NP-ELISA. The sensitivity is higher for NP-ELISA; therefore, all viral load parameters will be calculated using the data from NP-ELISA only.

A list of viral load parameters in respiratory samples that may be assessed (MITT population and subgroups) includes:

- Peak virus concentration by qRT-PCR
- Viral nasopharyngeal qRT-PCR AUC, BL to Day 5 and BL to Day 7 (baseline-adjusted and non-adjusted comparisons)
- Viral shedding by qRT-PCR versus time (baseline-adjusted and non-adjusted comparison)
- Percentage of subjects in whom peak qRT-PCR value occurred post-baseline
- Viral nasopharyngeal qRT-PCR AUC, BL to Day 7 and BL to Day 14
- Peak virus concentration by TCID50
- Percentage of subjects in whom peak TCID50 value occurred post-baseline Viral nasopharyngeal TCID50 AUC, BL to Day 5 and BL to Day 7

January 17, 2019

- For TCID50 AUC analyses (both the MITT population and the MITT population subset comprised of subjects with positive BL nasopharyngeal viral cultures); baseline-adjusted and non-adjusted comparisons.
- Viral shedding by TCID50 versus time (baseline-adjusted and non-adjusted comparison)
- Percentage of subjects with negative viral cultures by nominal study day (Day 3, Day 5, Day 7) (both the MITT population, and the MITT population subset comprised of subjects with positive BL nasopharyngeal viral cultures)
- Kaplan Meier analysis of time to resolution (negative) of viral cultures, by treatment arm (both the MITT population, and the MITT population subset comprised of subjects with positive BL nasopharyngeal viral cultures)

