-  If the subject has any history of delayed gastric emptying, including premenstruation syndrome or menstruation, he or she may receive oral premedications 120 minutes prior to IV VIS410/placebo infusion.
-  VIS410/placebo will be administered over 2 hours. Infusion time can be extended to up to 4 hours at discretion of the Investigator only if local infusion site-related symptoms occur.
-  Minimum of 10 doses of oseltamivir treatment (BID for 5 days) is required. Treatment with oseltamivir may be extended for up to 5 additional days (up to 20 doses of total therapy) if clinical symptoms warrant further treatment as assessed by the Investigator. Note: based on SOC, subjects may have started oseltamivir therapy prior to randomization. For patients unable to swallow, oseltamivir capsules can be opened and mixed with liquid for ease of administration.
-  To be obtained up to 2 hours post-VIS410 administration.
-  Nasopharyngeal swabs will be obtained for virology and/or PK from both nostrils (1 swab per nostril). The first 50 randomized subjects will have nasopharyngeal swabs collected up to Day 56 (predose, end of infusion, Days 3, 5, 7, 14, 28 and 56); while in the remaining subjects, nasopharyngeal swabs will be obtained up to Day 14 only.
-  If the subject remains in the hospital on Day 10, additional nasopharyngeal swabs will be obtained on Day 10.
-  One tracheal aspirate sample for virology and PK will be obtained (ventilated subjects only).

January 17, 2019

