14.3.5.10	Vital Signs – Summary of Not Done, Normal, Abnormal, and Clinically Significant	Safety
14.3.5.11	Vital Signs – Shift Tables of Not Done, Normal, Abnormal, and Clinically Significant	Safety
14.3.5.12	Summary of PCS Vital Sign Values	Safety
14.3.5.13	Electrocardiogram – Summary and Change from Baseline	Safety
14.3.5.14	Electrocardiogram - Summary of Normal and Abnormal Results	Safety
14.3.5.15	Electrocardiogram – Shift Table of Normal and Abnormal Results	Safety
14.3.5.16	Electrocardiogram – Categorical Summary of QTcF Changes	Safety
14.3.5.17	Physical Examination at Baseline Summary	Safety
14.4.1.1	Summary of Serum VIS410 Concentrations	PK
14.4.1.2	Summary of Serum VIS410 Pharmacokinetic Parameters	PK
14.4.1.3	Summary of Serum VIS410 Pharmacokinetic Parameters by ADA Status	PK
14.4.1.4	Summary of Nasopharyngeal VIS410 Concentrations	PK
14.4.1.5	Summary of Nasopharyngeal VIS410 Pharmacokinetic Parameters	PK

14.4.1.6	Summary of Nasopharyngeal VIS410 Pharmacokinetic Parameters by ADA Status	PK
14.4.1.7	Summary of Tracheal Aspirate VIS410 Concentrations	PK
14.4.1.8	Summary of Tracheal Aspirate VIS410 Pharmacokinetic Parameters	PK
14.4.2.1	Summary of Anti-influenza A Antibodies	MITT
14.4.2.2.1.1	Peak Viral Load (VL) Based on qRT-PCR from Nasopharyngeal Swabs Through Day 14	MITT
14.4.2.2.1.2	Peak Viral Load (VL) Based on qRT-PCR from Nasopharyngeal Swabs Through Day 14 by Subtype	MITT
14.4.2.2.1.3	Peak Viral Load (VL) Based on qRT-PCR from Nasopharyngeal Swabs Through Day 14 Subjects Positive for Viral Titer at Baseline	MITT
14.4.2.2.1.4	Peak Viral Load (VL) Based on qRT-PCR from Nasopharyngeal Swabs Through Day 14 Baseline Adjusted	MITT
14.4.2.2.2.1	Peak Viral Load (VL) Based on TCID50 from Nasopharyngeal Swabs Through Day 7	MITT
14.4.2.2.2.2	Peak Viral Load (VL) Based on TCID50 from Nasopharyngeal Swabs Through Day 7 by Subtype	MITT
14.4.2.2.2.3	Peak Viral Load (VL) Based on TCID50 from Nasopharyngeal Swabs Through Day 7 Subjects Positive for Viral Titer at Baseline	MITT
14.4.2.2.2.4	Peak Viral Load (VL) Based on TCID50 from Nasopharyngeal Swabs Through Day 7 Baseline Adjusted	MITT
14.4.2.3.1.1	Area Under the Viral Load-Time Curve (VL AUC) Based on qRT-PCR from Nasopharyngeal Swabs Through Day 14	MITT
14.4.2.3.1.2	Area Under the Viral Load-Time Curve (VL AUC) Based on qRT-PCR from Nasopharyngeal Swabs Through Day 14 by Subtype	MITT

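### The tested post-baseline peak viral load counts the end-of-infusion swab, which strongly dilutes the treatment contrast if viral load is already falling at dosing

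*SAP*

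**What the plan says.** SAP 9.2.8 (Nasopharyngeal Viral Load) states that "Differences between groups in peak post-baseline VL" will be tested for both assays, along with the proportion of subjects peaking after baseline. Its parameter list repeats the second item for qRT-PCR as "Percentage of subjects in whom peak qRT-PCR value occurred post-baseline", with a matching TCID50 entry. The sampling window for the peak is not defined, and no test is named for it.

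Four other statements settle, by default, which samples count:

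- SAP 4.1: "Baseline is defined as the latest non-missing measurement taken prior to study drug administration". Every later sample is therefore post-baseline.
- SAP 9.2.8, for all parameters except the proportion negative: "viral load will be assessed on all samples in the MITT population collected through Day 7" for TCID50, and through Day 14 for qRT-PCR.
- SAP 9.2.8, missing-data rule: "For missing data on Day 1 post-dose, Day 3, Day 5 and Day 7". The first swab after dosing is thus a recognised virology time point.
- SAP 16.2, footnote 26, on the end-of-infusion swab: "To be obtained up to 2 hours post-VIS410 administration". The next scheduled swab is on Day 3.

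Baseline-adjusted peak tables are also planned, for example Table 14.4.2.2.1.4, "Peak Viral Load (VL) Based on qRT-PCR from Nasopharyngeal Swabs Through Day 14 Baseline Adjusted". SAP 9.2.8 adjusts by dividing by the baseline value; the ANCOVA it mentions is an option for AUC only.

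On who is enrolled, Protocol 5.2.1 requires "Onset of influenza symptoms no more than 5 days before VIS410/placebo infusion". Protocol 5.2.2 allows up to six earlier antiviral doses, and every subject takes oseltamivir.

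**The concern.** A peak can show a drug effect only if the drug has had time to act before the peak is reached. The infusion lasts 2 hours and the swab follows within 2 hours of its end, so the swab falls about 2–4 hours after the infusion starts. With the permitted 4-hour infusion it can fall at about 6 hours. If viral load is already declining by then, the largest post-baseline value will usually be this early swab, and it will sit close to the predose level in every arm.

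The challenge study described in Protocol 1.3.2 was different. VIS410 was given 24 hours after inoculation, so a later peak could still be blunted; median peak TCID50 was 5.0 on placebo and 2.75 log10 on VIS410 (p = 0.009). Here, dosing may come up to 5 days after symptom onset.

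What is at stake is endpoint selection. Peak viral load is a named secondary endpoint, and the protocol synopsis says p-values will indicate which endpoints are most sensitive for Phase 3. An endpoint built so that it can hardly respond could be discarded for that reason alone.

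**Working it through.** The plan gives no power, effect size, decline rate or swab variability for these endpoints, so there is no figure of its own to reproduce.

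**Inputs from the documents:** 40 per arm, two-sided 0.05, swabs predose, at end of infusion and on Days 3, 5 and 7.

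**Assumptions, none from the documents:** log10 viral load = B − (d + e)t + noise. B has mean 6 and between-subject SD 1.0–1.5. Natural decline d is 0.3–0.8 log10/day. The added drug effect e (treated arm only, from time 0) is 0.25–0.5 log10/day. Swab SD is 0.3–1.0 log10. The end-of-infusion swab is at 3 h = 0.125 day, and Day 3 is at t = 2 days.

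**Central case by hand** (d = 0.5, e = 0.5, swab SD 0.6):

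- Expected arm difference at a single swab is e × t: 0.5 × 0.125 = 0.06 log10 at end of infusion, and 0.5 × 2 = 1.0 log10 on Day 3.
- SD of the difference between two swabs: 0.6 × √2 = 0.85.
- P(end-of-infusion swab exceeds predose), control: Φ(−0.5 × 0.125 / 0.85) = Φ(−0.07) = 0.47.
- P(end-of-infusion swab exceeds Day 3), control: Φ((1.0 − 0.0625) / 0.85) = Φ(1.10) = 0.86. Treated: Φ((2.0 − 0.125) / 0.85) = Φ(2.21) = 0.99.

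Simulation of 100,000 subjects per arm agrees (ranges are over B SD 1.0 and 1.5):

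| Central case | Swab counted | Day 3 onward |
|---|---|---|
| Arm difference in mean peak, log10 | 0.12 | 1.05 |
| Power, 40 v 40 | 0.05–0.07 | 0.83–0.98 |
| Proportion peaking post-baseline, control v treated | 0.49 v 0.44–0.45 | 0.12 v 0.01 |
| Power for the proportion | 0.06–0.07 | 0.53–0.54 |

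Hand check of one power figure: the simulated SD of the peak is 1.15, so SE = 1.15 × √(2/40) = 0.257 and power = Φ(0.12/0.257 − 1.96) = Φ(−1.49) = 0.07. This formula counts only rejections in VIS410's favour, which is why some values below fall under 0.05.

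**Whole grid, falling viral load:**

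- The end-of-infusion swab is the post-baseline peak in 56–100% of controls and 74–100% of treated subjects.
- The arm difference is 0.02–0.39 log10 with the swab and 0.49–1.30 from Day 3. Power at 40 v 40 is 0.03–0.26 and 0.28–0.99 respectively. For pooled VIS410 (80 v 40) it is 0.03–0.33 and 0.36–1.00.
- True pre-dose level explains 55–97% of the control-arm variance in the peak.
- The proportion peaking post-baseline is 0.40–0.62 v 0.35–0.54 (power 0.04–0.19). From Day 3 it is 0.00–0.43 v 0.00–0.25 (power 0.03–0.89).

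**Narrower grid** (d 0.3–0.5, e 0.2–0.4, swab SD 0.4–1.0, B SD 1.2, swab at 0.15 day): power is roughly 5–20% with the swab and 30–90% from Day 3. Adding baseline log10 viral load as covariate to the Day 3 version gives 46–100%. Adding it while keeping the swab gives only 6–26%, so the window is the main problem.

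**Sensitivity:**

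- Swab at 6 h (d = e = 0.5): it is still the peak in 70–98% of controls and 89–100% of treated subjects.
- 25–50% of subjects rising 0.5 log10/day for one more day (then control decline 0.5, drug effect 0.4): the swab is the peak in 69–91%, and power is 8–18% with it and 74–78% without.
- Viral load still rising in all controls through follow-up (d = −0.3, e = 0.8): the swab is the peak in 0–4% of controls and the arm difference is 1.9–2.0 log10, even with the swab counted.

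**The case against.** The strongest reply is that falling viral load is nowhere stated. Eligibility only caps symptom duration, early presenters can enrol, and the SAP plans subsets at 72 hours. When viral load keeps rising after dosing, the peak-value problem largely vanishes. This stands, and it makes the conclusion conditional. The condition is still a reasonable one for hospitalised subjects up to 5 days from onset, many of whom may already be on oseltamivir, and the loss persists when a quarter to a half of subjects rise for one more day.

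All the magnitudes are assumed, and that also stands. The model is a rougher guide for TCID50, where SAP 9.2.9 sets most below-limit values to zero.

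The trial is unpowered, p-values are informational, and AUC, by-visit viral load, proportion negative and time to resolution also capture antiviral effect. A reader might infer that the trial would miss an antiviral effect altogether; the documents do not support that. The risk is to the peak endpoints and to how they rank as Phase 3 candidates.

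Finally, under falling viral load a maximum from Day 3 onward is largely the Day 3 value, which is tabulated already. That is fair, but it is at least a post-treatment quantity and it captures later rises.

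**Conclusion.** The point holds as a conditional one. By the SAP's own definitions the end-of-infusion swab enters both tested peak endpoints. If viral load is falling at dosing in most subjects, the peak value mainly reflects pre-treatment level and the treatment contrast is strongly diluted: power is roughly 5–20% with the swab against 30–90% without it, under the narrower-grid assumptions. The proportion endpoint is then close to a coin toss.

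Three stronger readings are tempting but not supported:

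- That swab noise dominates both endpoints. It dominates the proportion only; the peak value is driven by between-subject differences in pre-treatment viral load.
- That the peak is a pre-effect value whatever the course of infection. This depends on the direction of viral load at dosing, which the documents do not give.
- That the baseline-adjusted peak must sit near 1. The SAP does not state the scale for the division. On raw values, swab SDs of 0.4–1.0 give a two-swab SD of 0.4√2 = 0.57 to 1.0√2 = 1.41 log10, so a ratio one SD either way runs from 0.27–3.7 to 0.04–26.

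**What to change.** In SAP 9.2.8:

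- Define the tested post-baseline peak, for qRT-PCR and TCID50, as the maximum over Day 3 and later samples within the existing Day 14 and Day 7 limits.
- Compare arms with baseline log10 viral load as covariate, in place of division by baseline.
- State whether the predose value enters the tabulated peak.
- Count a peak as post-baseline only when a Day 3 or later value exceeds both Day 1 values. Report this proportion descriptively, since it may be near zero in both arms.
- Say how these rules apply when predose is missing and the Day 1 post-dose value stands in for it.
- Keep the end-of-infusion swab in the by-visit summaries.

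The cost is SAP wording and programming, with no change to sampling. The small downside is that any effect in the first hours no longer enters the peak, though it stays visible by visit.

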**Changes from Previous Version of SAP**

SAP Version	Change from Previous Version	Reason	Revised SAP Sections
2.0	Population for Disposition Table 14.1.1.1 Changed from Enrolled to ITT	Change in analysis population	5.3, Appendix 16.6.1
	Details added regarding definition of baseline positivity based on viral load	Clarification of existing text	4.3, 9.2.10
	Addition of analysis based on mean VAS scores (summary table and figure) overall and in subsets based on time between symptom onset and treatment	Sponsor request	2.4.3, 3.3, 9.2.5
	Additional Subgroup added based on time between onset of symptoms and treatment	Subgroup for analysis of VAS scores	4.3
	Pairwise t-tests replaced by ANOVA based on ranks	Allows for contrast statements for all treatment comparisons utilizing all data	9.2.6
	Wilcoxon rank sum tests replaced by ANOVA based on ranks	Allows for contrast statements for all treatment comparisons utilizing all data	9.2.6
	Addition of summary analysis based on Sponsor-defined bacterial pneumonia	Complication of Influenza eCRF not correctly utilized	9.2.7
	Exact Mantel-Haenzel test and Cochran-Mantel-Haenzel test replaced by logistic regression	Allows for contrast statements for all treatment comparisons utilizing all data	9.2.1
	Additional details provided regarding the determination of anaphylaxis and hypersensitivity adverse events	Clarification of existing text	12.1

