## 2 STUDY DESIGN AND OBJECTIVES

### 2.1 Trial Design

This is a Phase 2b, multicenter, randomized, double-blind, controlled study comparing the efficacy and safety of 2 dose levels of VIS410 (2000 and 4000 mg) in combination with oseltamivir vs oseltamivir alone in hospitalized subjects with influenza A infection requiring oxygen support. Subjects will be randomly assigned at a ratio of 1:1:1 using a permuted block randomization method to receive VIS410 at a dose of 2000 mg (low dose) or 4000 mg (high dose) or placebo (0.9% sodium chloride), administered as a single IV infusion over 2 hours. Randomization will be stratified by presence or absence of positive pressure ventilation (PPV) at baseline to ensure an even distribution across treatment arms. All subjects will receive oseltamivir 75 mg twice daily (BID) for 5 days (total of 10 doses) as part of standard of care. Treatment with oseltamivir may be extended for up to 5 additional days (up to 20 doses of total therapy) if clinical symptoms warrant further treatment as assessed by the Investigator. Depending on standard of care, subjects may have started oseltamivir therapy prior to randomization. All subjects will also receive a pretreatment regimen of diphenhydramine 50 mg PO or IV plus either ibuprofen 400 mg PO or acetylsalicylic acid 320-325 mg PO approximately 60 minutes before infusion. Approximately 120 evaluable subjects (40/arm) with confirmed influenza A infection will be treated.

Study assessments are outlined in the Schedule of Assessments (copy in Appendix 16.2). Subjects discharged from the hospital prior to Day 14 will attend the applicable out subject follow-up visit(s) (e.g., Day 3, Day 5, Day 7, Day 14) per Table 1. The total study duration for each subject (screening through study exit) will be approximately 8 weeks (Day 56).

January 17, 2019

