### 9.2.10 Time to Resolution of Viral Load

Two analyses of median time to resolution of viral load, as determined by qRT-PCR or TCID50 results, and the 95% CI about the median, will be presented using Kaplan-Meier methods. Additional exploratory statistical analyses will be conducted to determine the differences in Kaplan-Meier curves using a log-rank test. Time to resolution of viral load will be assessed on all samples in the MITT population collected through the Day 7 visit for TCID50 analysis and

January 17, 2019

through the Day 14 visit for qRT-PCR analysis. For missing data on Day 1 post-dose, Day 3, Day 5, and Day 7, the analysis will be conducted without imputation and with the last observable measurement carried forward (LOCF). For missing data on Day 1 predose, the analysis will be conducted by replacing the missing data with the Day 1 post-dose observable measurement. Subjects missing both Day 1 predose and Day 1 post-dose virology data will be removed from the analysis. Resolution of viral load is considered to be one BLQ or lower measurement with no samples following that which are greater than the BLQ.

The following virology parameters will be derived:

- Time to resolution of viral load from end of infusion
  - Number of days from end of infusion until virus is no longer detectable (at or below the limit of detection) with no samples following that are greater than the BLQ through the Day 7 (TCID50) or Day 14 (PCR) visit
  - If virus is still above level of detection at Day 7 (TCID50) or Day 14 (PCR) visit, the value will be censored the on Day 7 visit for TCID50 or Day 14 (PCR)
- Time to resolution of viral load from onset of symptoms
  - Number of days from onset of symptoms until virus is no longer detectable (at or below the limit of detection) with no samples following that are greater than the BLQ through the Day 7 (TCID50) or Day 14 (PCR) visit
  - If virus is still above level of detection at Day 7 (TCID50) or Day 14 (PCR) visit, the value will be censored the on Day 7 visit for TCID50 or Day 14 (PCR)

The above analysis will also be performed for the MITT subset comprised of subjects with a positive baseline viral culture based on TCID50.

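### Viral negativity and time to viral resolution are tested without baseline viral load, although the SAP plans baseline-adjusted comparisons for viral AUC and shedding; adding it is cheap and may recover power

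*SAP*

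**What the plan says.** **Negativity.** SAP 9.2.8, on Days 3, 5 and 7: "Chi-square methods will be used to compare differences in treatment groups relative to placebo for the proportion of subjects with negative results". No covariate or stratum is named. The sentence covers comparisons with placebo only, whereas SAP 2.4.2 asks for four pairings, including 4000 mg v 2000 mg.

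**Time to resolution.** SAP 9.2.10 uses Kaplan-Meier estimates, with further exploratory analysis to "determine the differences in Kaplan-Meier curves using a log-rank test". Again no covariate is named.

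**Other read-outs of the same swabs.** SAP 3.2 and 9.2.8 ask for both baseline-adjusted and non-adjusted comparisons of viral AUC and of shedding over time. For AUC, dividing by baseline and then running ANOVA is a commitment. An ANCOVA is optional; of it the SAP says "The model will be evaluated with treatment as a fixed effect and baseline viral load as a continuous covariate".

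**Availability of baseline.** The Schedule of Assessments has a predose nasopharyngeal swab for all subjects. SAP 9.2.10 replaces a missing predose value by the Day 1 post-dose value and removes subjects with neither.

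**Testing framework.** SAP 4.1: "all statistical comparisons will be performed using 2-sided tests at the 0.05 significance level", p-values are informational, and "there will not be any adjustments for multiple comparisons". SAP 2.1 gives the size: "Approximately 120 evaluable subjects (40/arm) with confirmed influenza A infection will be treated". The protocol synopsis (Efficacy) says that p-values will indicate which endpoints are most sensitive to treatment differences.

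**The concern.** A sample is negative when viral load has fallen below a fixed limit, so a subject who starts high has further to fall. If baseline load predicts clearance, a test that ignores it treats explainable variation as noise. By design the comparison stays unbiased over repeated randomisations. In the one trial that is run, however, an arm that happens to start with lower titres will look better at clearing virus.

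What is at stake is the choice of endpoint. AUC and shedding will be reported with and without baseline adjustment, clearance only without. If p-values are then read across endpoints, clearance may look less sensitive than AUC partly because of how it was analysed.

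**Working it through.** The current plan states no power, negativity rate, hazard ratio or event count for viral clearance, so there is no figure to reproduce.

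**Inputs from the documents.** Two-sided 0.05; no multiplicity adjustment; 40 per arm, hence 40 v 40 per dose and 80 v 40 pooled; post-baseline swabs on Days 3, 5 and 7, that is 2, 4 and 6 days after infusion; culture follow-up censored at Day 7.

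**Assumed, because the documents are silent.** Negativity of 50% v 75%, 50% v 80% and 30% v 60%; correlation r between baseline and follow-up load of 0 to 0.7; clearance hazard ratio 2.0 or 2.5; placebo median 4 days; baseline effect g of 0 to 1.0 log-hazard per SD.

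**Step 1: unadjusted anchor.** Power = Φ[(|p1−p0| − 1.96·s0)/s1], where s0 is the pooled and s1 the unpooled standard error. For 50% v 75%, 40 v 40: s0 = √(2×0.625×0.375/40) = 0.1083; s1 = √((0.25+0.1875)/40) = 0.1046; (0.25 − 0.2122)/0.1046 = 0.362; power 0.641. The same formula gives 0.816 for 50% v 80% and 0.780 for 30% v 60%.

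**Step 2: negativity.** Follow-up load L = r·x + √(1−r²)·e, with x the standardised baseline; a sample is negative if L < Φ⁻¹(p for the arm). There were 3000 simulated trials per cell. Power, chi-square → logistic regression with baseline (likelihood-ratio test):

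| Setting | r = 0 | r = 0.3 | r = 0.5 | r = 0.7 |
|---|---|---|---|---|
| 40 v 40, 50% v 75% | 0.65→0.65 | 0.64→0.66 | 0.64→0.73 | 0.64→0.80 |
| 40 v 40, 50% v 80% | 0.81→0.82 | 0.82→0.86 | 0.82→0.88 | 0.81→0.94 |
| 40 v 40, 30% v 60% | 0.80→0.79 | 0.80→0.80 | 0.80→0.84 | 0.80→0.92 |
| 80 v 40, 50% v 75% | 0.77→0.77 | 0.79→0.81 | 0.79→0.85 | 0.78→0.91 |

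For 40 v 40, from the unrounded results, the gain is about 0 points at r = 0, 1 to 3 at r = 0.3, 4 to 9 at r = 0.5 and 12 to 16 at r = 0.7.

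**Step 3: time to resolution, 40 v 40.** Hazard = (ln 2/4)·exp(log HR·arm − g·x), seen only at the visits, 1500 trials per cell. Power, log-rank → Cox with baseline (Efron ties, Wald test):

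| HR | g = 0 | g = 0.35 | g = 0.7 | g = 1.0 |
|---|---|---|---|---|
| 2.0 | 0.77→0.75 | 0.68→0.72 | 0.55→0.66 | 0.42→0.59 |
| 2.5 | 0.95→0.94 | 0.91→0.93 | 0.80→0.91 | 0.67→0.85 |

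The gain is about 2 to 4, 10 to 12 and 17 to 18 points as g rises, with a loss of 1 to 2 points at g = 0. Type I error of the adjusted tests was 0.04 to 0.06 throughout.

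**Step 4: chance imbalance.** The difference in mean baseline between two arms of 40 has SD √(1/40+1/40) = 0.224 baseline SDs. At 50% negativity, a 1-SD imbalance shifts the observed rate by Φ(0.224r) − 0.5: 2.7, 4.5 and 6.2 percentage points at r = 0.3, 0.5 and 0.7. The unadjusted test's error rate already allows for this; its point estimate does not correct for it.

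**The case against.** The strongest reply is that nothing is broken. The trial is declared exploratory and unpowered, p-values are informational, the log-rank test is itself labelled exploratory, and both endpoints are repeated in the baseline culture-positive subset. This largely stands, and it limits the point to efficiency. It does not remove it, because the protocol still ranks endpoints by p-value. The subset conditions on being positive, not on how high the titre is, and it uses fewer subjects.

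Several stronger readings are tempting but unsupported:

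- *That the SAP already uses baseline load as a covariate for AUC.* Only division by baseline is committed; the ANCOVA may be used.
- *That influenza subtype is ignored.* SAP 9.2.8 summarises the proportion negative per subtype and lists H1N1 v H3N2 subset analyses. SAP 16.6.1 has by-subtype tables for percent negative (14.4.2.6.2, 14.4.2.7.2) and time to resolution (14.4.2.4.2, 14.4.2.5.2). Subtype is absent only from the pooled test.
- *That pooled culture results mix read-outs of different sensitivity.* The SAP says of H3: "The sensitivity is higher for NP-ELISA; therefore, all viral load parameters will be calculated using the data from NP-ELISA only". That compares two read-outs within H3. Nothing is said about H1, so unequal sensitivity cannot be inferred.
- *That SAP 2.0 set a precedent for baseline adjustment.* The change log says "Exact Mantel-Haenzel test and Cochran-Mantel-Haenzel test replaced by logistic regression", but the reason given is contrasts using all data, and that model adjusts for randomisation strata.
- *That the gain is known to be large.* A titre model with true baseline SD (s) 1.2 to 1.8 log10, swab error SD (e) 0.7 to 1.0 and one decline rate shared by all subjects in an arm implies r = s²/(s²+e²), from 1.44/2.44 = 0.59 to 3.24/3.73 = 0.87. If decline rates vary between subjects with SD 0.75 log10 per day, two days add variance (2×0.75)² = 2.25, and r falls to 1.44/√(2.44×4.69) = 0.43 and 3.24/√(3.73×5.98) = 0.69. All these inputs are assumptions.

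**Conclusion.** The point holds as a cheap improvement, not as an error. Both clearance comparisons are unadjusted as written, the baseline value is available, and the SAP treats AUC and shedding differently. For 40 v 40, adjustment gains about 0 points of power if baseline load is not prognostic (for the Cox model, a loss of up to 2), a few points if weakly prognostic, and about 10 to 18 if strongly prognostic. The direction is reliable wherever baseline predicts clearance. The size rests on a correlation that the documents do not give.

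A reader might infer that the planned tests are invalid or that a stated power is missed. Neither follows: the tests hold their error rate, and the plan claims no power.

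**What to change.** **SAP 9.2.8.** Add logistic regression of negative/positive at Days 3, 5 and 7 on treatment and baseline log10 viral load, with contrasts for the four pairings of SAP 2.4.2. Use a score or penalised test where cells are sparse.

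**SAP 9.2.10.** Add a Cox model with the same covariate. SAP 9.2.2 already plans a covariate-adjusted Cox model for oxygen cessation.

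**Coding of baseline negatives.** SAP 9.2.9 sets qRT-PCR negatives to zero. For TCID50 it sets the first below-limit value to half the limit, and later ones and untested PCR-negatives to zero. State how these enter the covariate, for example as a fixed value below the limit plus a baseline-negative indicator. Say also how post-dose substitutes for a missing predose value are treated, and report any subjects lost for lack of a baseline.

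**Optional.** Add subtype as a factor in the pooled models.

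**Keep** the chi-square percentages, Kaplan-Meier curves and log-rank test as supportive. Adjusted odds and hazard ratios are conditional on baseline, so they are on a different scale from the unadjusted contrasts and should be labelled as such.

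**Cost.** SAP wording and a few extra models; no new data. The downside is more output and the change of estimand scale.
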